4.1 Description of study design

This is a randomized, double-blind, multi-center, placebo-controlled phase III study of midostaurin (PKC412) or placebo in combination with idarubicin/daunorubicin and cytarabine for induction therapy, intermediate-dose cytarabine for consolidation therapy, followed by post-consolidation therapy with midostaurin or placebo in adult patients with newly diagnosed FLT3-MN (SR<0.05) AML, i.e., FLT3 mutant to wild type signal ratio below the 0.05 clinical cut-off. The study is designed to evaluate the efficacy and safety of midostaurin combined with intensive chemotherapy in this indication. 502 adult patients with newly diagnosed AML demonstrating FLT3-MN (SR<0.05) as determined by a Novartis designated laboratory will be enrolled at approximately 150-180 sites worldwide.

Figure 4-1 Study Design

Eligible and consented patients are allowed to start with the 7+3 chemotherapy immediately after the unequivocal diagnosis of AML; the day of the first dose of chemotherapy is defined as Day 1.

Patients will be tested for the absence of FLT3-ITD and FLT-TKD mutations, using a validated clinical trial assay in a Novartis designated laboratory. Absence of mutation is defined as ITD and TKD activating mutations at codons D835 and I836 in the FLT3 gene, below the clinical cutoff of 0.05 mutant to wild type signal ratio.

Patients with confirmed FLT3-MN (SR<0.05) AML will be randomly assigned 1:1 to midostaurin or placebo by using a stratified randomization according to age (<60 vs. ≥60 years), Patients will be randomized on Day 8, i.e., the day of the first dose of midostaurin or placebo. Patients with a FLT3 mutation or with an unknown FLT3 mutation status by study Day 8 will be considered as molecular screening failures and cannot be randomized.

Provided that FLT3-MN (SR<0.05) status has been confirmed, patients meeting all other eligibility criteria will start the administration of midostaurin or placebo on Day 8.

4.2 Study phase (details of dosing in section 6)

The study contains three treatment phases:

- Induction treatment phase
- Consolidation treatment phase and,
- Post-consolidation treatment phase

A patient has to meet the following criteria to continue with the next treatment phase:

- A patient achieves CR at end of any treatment phase OR patient achieves CRi at end of any treatment phase **with adequate blood count recovery** defined as the following:
 - Complete Recovery in neutrophil count ($\geq 1 \times 10^9/L$)
 - Minimal recovery in platelet count ($\geq 50 \times 10^9/L$)

Of note, a patient not meeting the above criteria up to 93 days after start of induction phase is considered as “*induction failure*”. For details please see [Section 7.2.1.1](#).

The planned duration of an induction and consolidation cycle is 28 days. Upon adequate blood count recovery after day 28, midostaurin is stopped immediately (e.g., the evening dose of midostaurin or placebo on that day is not taken). Forty-eight hours thereafter is Day 1 (and start of chemotherapy) of the next cycle (Induction 2, Consolidation 1-4). At the end of the last consolidation cycle, i.e., prior to start of the post-consolidation cycle 1, midostaurin or placebo will not be interrupted. The duration of each post-consolidation cycle is 28 days.

4.2.1 Induction phase

All patients will receive at least one cycle of induction therapy with continuous infusion cytarabine and idarubicin/daunorubicin. Patients not achieving CR nor CRi with adequate blood count recovery after induction 1 will receive a second cycle with intermediate-dose cytarabine and daunorubicin/idarubicin (the latter only in patients under 60 years of age).

Daunorubicin may be replaced by an equivalent dose of idarubicin.

The dose of idarubicin would be one fifth of the planned daunorubicin dose. Midostaurin will start on day 8 of the first induction cycle and last until 48 hours before the start of the next chemotherapy cycle which is either a second induction or the first consolidation cycle.

Patients achieving CR or CRi with adequate blood count recovery with induction cycle 1 will go directly to consolidation therapy (4 cycles) without a second cycle of induction therapy. Patients who do not achieve CR nor CRi with adequate blood count recovery with one cycle

of induction will receive a second induction cycle with intermediate dose cytarabine and daunorubicin/idarubicin.

Patients achieving CR or CRi with adequate blood count recovery with 2 cycles of induction will go directly to consolidation therapy (3 cycles).

Patients not achieving CR nor CRi with adequate blood count recovery after induction 2 (i.e. up to 93 days after start of induction phase) will discontinue study treatment and will be followed for survival.

4.2.2 Consolidation phase

Patients achieving CR or CRi with adequate blood count recovery after induction with one or two cycles of induction therapy will proceed to consolidation therapy with either 3 or 4 cycles of intermediate-dose cytarabine respectively, or to HSCT with or without preceding consolidation cycles. Patients may undergo transplantation at the discretion of the Investigator (refer to 2017 ELN and 2016 National Comprehensive Cancer Network (NCCN) recommendations). In patients who are treated with allogeneic HSCT instead of consolidation therapy or after start of consolidation therapy the conditioning regimen and management after transplantation will be according to local institutional standards. Study treatment will be interrupted at least 48 hours before the initiation of the transplant conditioning regimen. Patients with transplantation and recovery from the procedure will not receive further cycles of consolidation treatment but receive post-consolidation treatment with study drug. They can start the post-consolidation therapy not earlier than 30 days after transplant but not later than 100 days after transplant.

Patients will receive midostaurin (two 25 mg capsules) or placebo (2 capsules) twice daily orally from day 4 until 48 hours prior to the start of the next consolidation cycle.

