A bone marrow aspiration will be performed in all patients between Day 21-28 to determine the need for a second induction cycle. If the bone marrow aspirate is insufficient to make a determination of remission, then the bone marrow assessment should be repeated after about one week.

A disease assessment will be performed at the end of induction 1 based on bone marrow and peripheral blood assessments. If the response is CR or CRi with adequate blood recovery the patient will proceed to the consolidation phase. If the response is CRi without adequate blood count recovery, the patient will continue to be treated with Midostaurin/Placebo and observed up to 2 weeks to get the platelet $\geq 50 \times 10^9/L$ and neutrophil $\geq 1 \times 10^9/L$ (i.e., adequate blood count recovery) to be able to move to consolidation. In such cases a response assessment will be performed at day 42 (28 days plus the time window of 2 weeks for adequate blood count recovery)

If patients after induction 1 therapy still show $\geq 5\%$ blasts (i.e., no CR or CRi) in their D21-D28 bone marrow, then they require a second induction treatment. Dosing of midostaurin/placebo should be stopped immediately after knowledge of $\geq 5\%$ blasts persistence. 48 hours thereafter the second induction treatment should start.

Of note, Physicians should consider earlier bone marrow exams in patients whose peripheral blood counts are not recovering or recovering in an unexpectedly slow manner.

Second Induction:

Patients who still have more than $\geq 5\%$ blasts in their bone marrow (no CR or CRi) after induction cycle 1 require a second induction treatment. Dosing of midostaurin/placebo should be stopped immediately. 48 hours thereafter the second induction treatment should start.

- **Intermediate-dose cytarabine (IDAC)** 1500 mg/m² will be administered by intravenous infusion over 3 hours every 12 hours on Day 1 to 3. Serial neurologic evaluations will be performed before and following the infusion of intermediate-dose cytarabine. **For patients of age 60 years or older at the time of study entry a dose of 1000 mg/m² will be administered.**
- **Daunorubicin** 50 mg/m²/day *or* **idarubicin** 10 mg/m²/day will be administered intravenously by IV push (IVP) or short (30 minute) infusion on Day 1-3 **for patients <60 years only. Patients ≥ 60 years at the time of study entry will not be given daunorubicin *or* idarubicin**

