- **Study drug (midostaurin** 50 mg [two 25 mg capsules] **or placebo** [2 capsules]) will be administered twice per day by mouth from Day 4 until 48 hrs prior to start of next cycle (i.e. the morning of Day 27 if hematopoiesis recovers timely (cycle length of 28 days) or later if the cycle needs to be prolonged for blood count recovery).).

A bone marrow aspiration will be performed in all patients between Day 21-28 to determine if the patient can move to consolidation phase. If the response is CR, the patient will proceed immediately after Day 28 to the consolidation phase. If the response is CRi without adequate blood count recovery, the patient will continue to be treated with Midostaurin/Placebo and observed 3 additional weeks for an adequate blood recovery to be able to move to consolidation. If no adequate blood count recovery will be achieved after these 3 additional weeks, the patient will be discontinued from treatment and followed for survival. Otherwise, the patient will move to consolidation. A response assessment will be performed at day 49 (28 days plus the time window of 3 weeks for adequate blood count recovery). **Patients who failed to achieve CR or CRi with adequate blood count recovery after a second induction will be discontinued from protocol** therapy and followed for survival and post-study-treatment therapies ([Section 7.1](#)).

Consolidation (3 or 4 cycles)

Patients achieving a CR or CRi with adequate blood count recovery after induction 1 will receive 4 cycles of consolidation therapy with midostaurin/placebo + chemotherapy.

Patients achieving a CR or CRi with adequate blood count recovery only after induction 2 will receive 3 cycles of consolidation therapy with midostaurin/placebo and chemotherapy.

A bone marrow examination must be performed at each cycle of the consolidation phase to evaluate for relapsed AML.

- **Intermediate-dose cytarabine (IDAC)** 1500 mg/m² will be administered by intravenous infusion over 3 hours every 12 hours on Days 1 to 3. Serial neurologic evaluations will be performed before and following the infusion of intermediate-dose cytarabine. **For patients of age 60 years or older at the time of study entry a dose of 1000 mg/m² will be administered .**

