6.1.5 Treatment duration

The treatment consists of 3 treatment phases and the maximum planned duration of treatment is 17 cycles. Planned durations of each treatment phase are:

- **Induction phase:** 1 or 2 cycles (daunorubicin/idarubicin, cytarabine and midostaurin/placebo). The maximum length of the first induction cycle is 43 days (28 days plus potentially up to 14 additional days for adequate blood count recovery plus 1 day prior to the start of the next cycle. Patients not achieving CR or CRi after Induction 1 will

get a second cycle of Induction. The maximum length of the second induction cycle is 50 days (28 days plus potentially up to 21 additional days for adequate blood count recovery plus 1 day prior to the start of the next cycle).

- **Consolidation phase:** Patients who achieved CR or CRi with adequate blood count recovery after induction 1 therapy will receive 4 cycles of consolidation (intermediate-dose cytarabine and midostaurin/placebo). Patients achieving CR or CRi with adequate blood count recovery only after induction 2 therapy will receive 3 cycles of consolidation. One cycle length is planned to be 28 days whereas the maximum length of each consolidation cycle is 50 days (28 days plus potentially up to 21 additional days for adequate blood count recovery plus 1 day prior to the start of the next cycle).
- **Post-consolidation phase :** 12 cycles (midostaurin/placebo). Each cycle is 28 days.

Patients may be discontinued from treatment prior to completion of study therapy for reasons of unacceptable toxicity, induction failure, relapse from CR/CRi with adequate blood count recovery, withdrawal of consent, failure to abide by the protocol, or at the discretion of the investigator.

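### Protocol section 4.2.2 reverses the number of consolidation cycles: it gives 3 after one induction and 4 after two, where the rest of the protocol gives 4 and 3

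*Protocol*

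**What the plan says.** Protocol section 4.2.2 (Consolidation phase) states that patients in CR, or in CRi with adequate count recovery, after "one or two cycles of induction therapy will proceed to consolidation therapy with either 3 or 4 cycles of intermediate-dose cytarabine respectively", or go to transplant with or without preceding consolidation cycles.

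Four other sections give the number of consolidation cycles separately for each induction path:

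- **4.2.1:** responders "with induction cycle 1 will go directly to consolidation therapy (4 cycles"); responders "with 2 cycles of induction will go directly to consolidation therapy (3 cycles").
- **6.1.1.1, Consolidation:** patients in remission "after induction 1 will receive 4 cycles of consolidation therapy", and those who reach it "only after induction 2 will receive 3 cycles of consolidation therapy".
- **6.1.5:** 4 cycles for responders to induction 1; patients responding "only after induction 2 therapy will receive 3 cycles of consolidation". The same section sets a planned maximum of 17 cycles in total, 12 of them post-consolidation.
- **7.1.3:** 4 cycles after the first induction cycle, 3 after the second.

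The Study design entry of the protocol summary has a sentence close to the one in 4.2.2 but without the word *respectively*. Section 2.4 says three or four cycles. Neither states a pairing, so neither conflicts with the four sections above.

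**The concern.** The word *respectively* ties the first number in each pair together and the second number in each pair together, so 4.2.2 can only be read as 3 consolidation cycles after one induction and 4 after two. That is the reverse of the rule stated everywhere else.

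This is an instruction on how much cytotoxic chemotherapy to give, placed under the heading where a reader would look for the consolidation rule. The consolidation row of Table 6-1 gives dose and days but no cycle count, so that table would not correct a misreading. A site acting on 4.2.2 would give one intermediate-dose cytarabine cycle too few after one induction, or one too many after two. The extra cycle would go to patients who had already needed a second induction.

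The contradiction also touches the description of treatment compliance. Protocol section 12 allows no authorised deviations. SAP sections 4.5 and 5 call for counts of patients completing each treatment phase according to protocol and for a tabulation of deviations. A patient with one induction and three consolidation cycles is complete under 4.2.2 and one cycle short under 6.1.1.1.

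**Working it through.** **Inputs**

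- Consolidation cycles after one and after two inductions: 3 and 4 (4.2.2); 4 and 3 (4.2.1, 6.1.1.1, 6.1.5, 7.1.3).
- Post-consolidation: 12 cycles (6.1.5).
- Planned maximum: 17 cycles (6.1.5).
- Cytarabine in induction 2: 1500 mg/m² per dose, or 1000 mg/m² at age 60 or over; it "will be administered by intravenous infusion over 3 hours every 12 hours on Day 1 to 3" (6.1.1.1). Consolidation uses the same doses and schedule.
- Cytarabine in induction 1: a continuous standard-dose infusion, so not counted as intermediate-dose.

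**Step 1. Reproduce the 17-cycle maximum**

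Total cycles = induction + consolidation + 12.

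| Pairing | One induction | Two inductions | Maximum |
|---|---|---|---|
| 4 and 3 (four sections) | 1 + 4 + 12 = 17 | 2 + 3 + 12 = 17 | 17, as stated |
| 3 and 4 (4.2.2) | 1 + 3 + 12 = 16 | 2 + 4 + 12 = 18 | 18, one above the stated limit |

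The protocol's figure is reproduced with 4 and 3, and exceeded with 4.2.2 as written.

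**Step 2. Count intermediate-dose cytarabine cycles**

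Induction 2 is itself an intermediate-dose cycle.

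- 4 and 3: 4 cycles after one induction; 1 + 3 = 4 after two.
- 4.2.2 as written: 3 cycles after one induction; 1 + 4 = 5 after two.

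**Step 3. Convert to dose**

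Two doses a day for 3 days is 6 doses per cycle:

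- under 60: 6 × 1500 = 9,000 mg/m² per cycle;
- 60 or over: 6 × 1000 = 6,000 mg/m² per cycle.

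Cumulative intermediate-dose cytarabine if all cycles are completed (mg/m²):

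| Age | Path | 4 and 3 | 4.2.2 as written | Difference |
|---|---|---|---|---|
| Under 60 | One induction | 4 × 9,000 = 36,000 | 3 × 9,000 = 27,000 | −25% |
| Under 60 | Two inductions | (1 + 3) × 9,000 = 36,000 | (1 + 4) × 9,000 = 45,000 | +25% |
| 60 or over | One induction | 4 × 6,000 = 24,000 | 3 × 6,000 = 18,000 | −25% |
| 60 or over | Two inductions | (1 + 3) × 6,000 = 24,000 | (1 + 4) × 6,000 = 30,000 | +25% |

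**The case against.** The strongest reply is that this is one misordered pair of numerals in an overview section, and that a site is unlikely to act on it. The parent heading reads "Study phase (details of dosing in section 6"), section 6 states the correct rule twice, 4.2.1 gives it immediately above, and 7.1.3 repeats it. The documents report no site that misread the text. All of this stands, and it limits the practical risk.

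The dose figures are also a worst case. They need a site to follow 4.2.2 over the other sections and a patient to complete every consolidation cycle. Patients going to transplant receive fewer cycles by design, and Table 6-2 allows cytarabine to be reduced or stopped. This stands too: the 25% figures describe the consequence of following the sentence, not an expected effect in the trial.

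The 17-cycle argument has a limit. It rules out 4 consolidation cycles after two inductions, but on its own it would also allow 3 after one and 3 after two (totals of 16 and 17). That is correct as arithmetic, but no section proposes 3 and 3. Between the two pairings that the protocol contains, only 4 and 3 fits. The 4 cycles after one induction rest on the explicit statements in the four sections. The equal count of intermediate-dose cycles under 4 and 3 is supporting evidence only, since the protocol does not give it as a reason.

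Finally, the SAP introduction records that the study was stopped for futility on 23-Sep-2019 and that most patients left within weeks. A correction now mainly serves the accuracy of the record and the treatment description in the study report. None of these points makes the sentence in 4.2.2 right.

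**Conclusion.** The concern holds. Section 4.2.2 states the consolidation rule the wrong way round, and four other sections, together with the 17-cycle maximum, identify it as the text in error.

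The size is one intermediate-dose cytarabine cycle per patient in either direction: 9,000 mg/m² under age 60 or 6,000 mg/m² at 60 or over, a quarter of the intended cumulative dose. This assumes that 4.2.2 is followed literally and that all consolidation cycles are completed.

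The slip should be corrected because it sits in an operative chemotherapy instruction, although the correct text nearby and in section 6 makes misuse unlikely. The definitions of EFS and OS, their tests, the alpha and the event targets do not depend on it.

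**What to change.** In section 4.2.2, change the order of the two numerals so that one or two induction cycles are followed by 4 or 3 consolidation cycles, respectively. The word *respectively* can then stay. The protocol summary and section 2.4 need no change. Adding the cycle counts to the consolidation row of Table 6-1 would help but is optional, because 6.1.1.1 already states them.

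The cost is two numerals. No design element, sample size or analysis changes.

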4.2.3 Post-consolidation phase

After adequate blood count recovery following the final cycle of consolidation therapy, patients will receive 12 cycles (28 days/cycle) of continuous therapy with midostaurin or placebo twice daily at 50 mg.

Patients who underwent HSCT after achieving CR or CRi with adequate blood count recovery will receive midostaurin or placebo 50 mg twice daily as post-consolidation therapy, continuously, for up to 12 cycles (28 days/cycle). Post HSCT post-consolidation therapy will begin >30 days but not later than 100 days following HSCT.

4.2.4 Follow-up phase

Patients who discontinue study treatment will continue to have response assessments performed every 12 weeks until documented relapse, and thereafter will be followed every 3 months for survival except those who are lost to follow-up. Data on anti-neoplastic therapies will be collected as well.

4.3 Timing of interim analyses and design adaptations

Two interim analyses are planned when approximately 114 and 214 of the 285 EFS events targeted for the primary analysis (approximately 40% and 75% information fraction, respectively) have been documented. The first interim analysis is planned for a futility assessment. The study can be stopped for efficacy at the second interim analysis. These analyses are expected to take place around 12 and 20 months, respectively, from the date of first patient randomized in the study assuming an increasing recruitment rate to reach 30 patients/month 6 months after start of the study. Please refer to [Section 10.7](#) for detailed information.

4.4 Definition of end of study

The end of study will occur when approximately 278 deaths have been documented (it is estimated that these 278 deaths will be observed at approximately 64 months from the date of randomization of the first patient) or 5 years after the end of the study treatment for the last patient whichever occurs first. At this time, the final OS analysis will be performed. All patients will remain in treatment, post-treatment or survival follow-up until the data cut-off date and all available data up to this cut-off date will be analyzed.

4.5 Early study termination

[figure not shown]
The study may be terminated at any time for any reason by Novartis. This may include reasons related to the benefit/ risk assessment of participating in the study, practical reasons (including slow enrollment), or for regulatory or medical reasons. In taking this decision to terminate, Novartis will always consider the subject's welfare and safety. Should this be necessary, patients should be seen as soon as possible for the End of Treatment (EOT) visit, and assessments for EOT as described in [Section 7](#) should be performed for discontinued or withdrawn patients. The investigator may be informed of additional procedures to be followed in order to ensure that adequate consideration is given to the protection of the patient's interests. The investigator will be responsible for informing institutional review boards (IRBs) and/or ethics committees (ECs) of the early termination of the trial.

In the event that the study is terminated prematurely, e.g., due to futility or overwhelming efficacy, patients still receiving study treatment and who, according to investigator assessment, continue to benefit from the treatment, will be offered to complete study treatment as per protocol.

5 Population

5.1 Patient population

The study population will be comprised of male and female patients ≥ 18 years of age with newly diagnosed FLT3-MN (SR<0.05) (no ITD in the juxtamembrane domain or TKD activating mutation as defined in inclusion criteria) AML who are deemed by the investigator to be suitable for treatment with intensive induction and consolidation chemotherapy.

All data for the Inclusion/Exclusion criteria must be verifiable in the patient's source documents.

